### 7.2.1. Subject Population Rationale

The goal of the study is to recruit subjects with a clearly identifiable primary traumatic event during adulthood.

Inclusion criterion #2 clarifies that subjects with delayed-onset PTSD (i.e., the full diagnostic criteria for PTSD are not met until at least 6 months after the event, although the onset and expression of some symptoms may be immediate) (APA 2013) will be allowed to enter into the study if the full diagnostic criteria for PTSD according to the DSM-5 are met at least 6 months prior to screening.

In delayed-onset PTSD, which occurs in about 25% of PTSD cases, (Utzon-Frank 2014) subjects might have experienced subthreshold PTSD symptoms after the trauma. Potentially, some additional trauma then impairs the individual's ability to cope with the index traumatic event. Consequently, subthreshold PTSD symptoms become more severe and evolve into clinically manifest PTSD. For inclusion into the study, at least 6 months of clinically manifest PTSD must be present prior to screening (inclusion criterion #2), with no further traumas in that same 6-month period (exclusion criterion #4).

Subjects meeting inclusion criteria #2, #3 and #4 enrich the study with a moderate-to-severe PTSD population. A score of 38 or higher on PCL-5 indicates likely PTSD in both civilian and veteran populations. (Blevins 2015, Hoge 2014) The timeframe associated with the primary traumatic event as defined by inclusion criterion #2 is designed to minimize spontaneous remission during the study, while exclusion criteria #1, #3, and #4 control for significant chronicity of the disease and minimize Axis-II disorders overlapping with associated complex traumas in childhood. Exclusion criterion #1 reduces the variability of the study population by excluding subjects with complex PTSD. Subjects with complex PTSD typically present with psychological symptoms related to prolonged, repeated trauma, and these are often present in addition to the more typical symptoms of PTSD, including changes in self-concept and response to stressful events. Although "complex PTSD" is not an established diagnostic category in the DSM-5, this protocol helps navigate identification of complex PTSD based on trauma type, age of subject when exposed to trauma, and certain phenotype (i.e., if affect dysregulation and interpersonal dysfunction are primary over other core PTSD symptoms).

Exclusion criteria #6, #7, #9, #14, and #16 minimize disease comorbidities, and #5 minimizes TBI consequences associated with the primary traumatic event. The purpose of exclusion criteria #10, #11, #12, and #13 is to exclude subjects taking psychoactive drugs due to either their potential influence on PTSD symptoms (different classes of antidepressants, sleep inducers with long half-life) or potential interference with NYX-783 influencing the effect of NMDA modulation on sleep architecture, interference with the pharmacology of NYX-783 (i.e., there is a possible interaction between gabapentinoids [pregabalin, gabapentin], interaction with and certain NMDA receptor complexes). (Chen 2018)

### **7.3. Justification of Dose**

The planned dose levels in this study are NYX-783 50 mg/day and 10 mg/day. Based on the preliminary PK results of the Phase 1, first-in-human study in healthy male and female volunteers (NYX-783-1002), the maximum plasma concentration ( $C_{max}$ ) of NYX-783 50 mg is expected to be approximately 0.8  $\mu\text{g/mL}$ . Total exposure (area under the plasma-concentration curve [ $AUC_{0-24}$ ]) is expected to be approximately 5.0  $\mu\text{g}\cdot\text{h/mL}$ .

In the contextual fear conditioning test, NYX-783, when administered to rats as a single oral dose of 1 mg/kg, facilitated fear extinction learning on extinction Days 1-4 and prevented the

re-consolidation of fear memory when retested on Day 14 compared to vehicle. At this pharmacologically-active dose (1 mg/kg) in rats, the plasma  $C_{max}$  is calculated to be 0.5  $\mu\text{g/mL}$ .

In addition, a single dose of NYX-783 in the fear conditioning stress model provided a long-term effect, preventing freezing behavior after one dose of drug in rodents and preventing recovery of fear after 14 days. One objective of this Phase 2 study is to confirm that the observed preclinical long-lasting effects are translatable to humans, i.e., once daily (QD) administration provides long-lasting benefits.

The pharmacologic effects of NYX-783 are currently believed to be driven primarily by  $C_{max}$ . Thus, the dose planned for the current clinical study is expected to result in human plasma concentrations that are within the  $C_{max}$  range that was associated with positive effects on -fear extinction measures.

The 50 mg dose is 1/12th of the maximum single dose (600 mg) and 25% of the maximum multiple dose (200 mg) given once daily for 7 days in the Phase 1 trial (NYX-783-1002), which were safe and well-tolerated. The 600 mg single dose as well as the 200 mg multiple dose were associated with PK exposures ( $C_{max}$  and AUC) below the NOAEL for both the dog and rat in the Good Laboratory Practice toxicology studies. In the Phase 1 trial, NYX-783 had a terminal elimination half-life ( $t_{1/2}$ ) of approximately 4 hours and demonstrated no accumulation with once daily dosing over 7 days. In all single-dose groups, approximately 57% of the administered dose was recovered as NYX-783 in the urine. Based on the available preclinical and preliminary clinical safety and PK data, the 10 and 50 mg dose strengths selected for this study are expected to be safe and well-tolerated.

## **8. SELECTION AND WITHDRAWAL OF SUBJECTS**

### **8.1. Subject Inclusion Criteria**

In order to be eligible to participate in this study, an individual must meet all of the following criteria:

1. Male and female subjects between the ages of 18 to 65 years (inclusive) at the time of signing the informed consent.
2. A primary diagnosis of PTSD (DSM-5 criteria, APA 2013) according to the CAPS-5 and SCID-5-CT, with the primary traumatic event occurring  $\geq 12$  months prior to screening. NOTE: In cases of “delayed--onset PTSD,” clinically manifest PTSD symptoms must be present for at least 6 months prior to screening.
3. PCL-5  $\geq 38$  at screening.
4. CAPS-5 total score  $\geq 30$  at screening.
5. Qualified to participate according to the SAFER interview.
6. Female subjects of childbearing potential must have a negative serum pregnancy test at screening and be practicing an adequate method of birth control (e.g., oral or parenteral contraceptives, intrauterine device, barrier, abstinence). Subjects may not be breastfeeding or plan to become pregnant or donate ova during the study and for 30 days after the last dose of study drug.
7. Male subjects who are sexually active with female partner(s) must agree to the following during the study and for 30 days after the last dose of study drug: a) use an acceptable method of birth control (condom with spermicide or surgical sterilization) and b) refrain from sexual activity with female partners who do not use an acceptable method of birth control. Barrier contraception (condom with spermicide) **must** be used by all male subjects who are not surgically sterilized at least 90 days prior to screening. Male subjects must also agree to refrain from sperm donation during the study and until 30 days after the last dose of study drug.
8. Ability to understand the requirements of the study, provide written informed consent, abide by the study restrictions, and agree to return for the required assessments.
9. Willing to use a smartphone-based video recording technology for monitoring compliance with study drug administration.
10. The subject has a stable social situation in the investigator’s opinion, e.g. no changes are expected during the course of the study in work, marital, or accommodation status.

### **8.2. Subject Exclusion Criteria**

An individual who meets any of the following criteria will be excluded from participation in this study:

1. Complex PTSD, defined as a condition that may develop following exposure to an event or series of events of an extreme and prolonged or repetitive nature of which the subject experienced as extremely threatening or horrific and from which escape was difficult or

impossible (e.g., torture, slavery, genocide campaigns, prolonged domestic violence, repeated childhood sexual or physical abuse). If affect dysregulation and interpersonal dysfunction that are primary over other core PTSD symptoms, in the investigator's opinion, they should be considered as exclusionary criteria. NOTE: Non-interpersonal trauma (e.g. motor vehicle accident, mass transportation accident, domestic fire, mass shooting survivor) prior to 18 years of age are not exclusionary, and, the trauma can be considered the primary traumatic event (index trauma).

2. Trauma focused psychotherapies including, prolonged exposure therapy, cognitive behavioral therapy, eye movement desensitization and reprocessing therapy (EMDR) within 30 days prior to screening or during the study.
3. Primary traumatic event occurred prior to 2001.
4. Primary traumatic event was followed by further major traumatic life episodes in the 6 months prior to screening.
5. Primary traumatic event was associated with traumatic brain injury (TBI) categorized as Moderate-to Severe TBI, according to the Mayo TBI Severity Classification System. (Malec 2007) (See Appendix A)
6. Substance use disorder within the 6 months prior to screening. Use of any illicit drugs of abuse during the study period is prohibited.
7. History of alcohol abuse within the 6 months prior to screening. NOTE: Up to an average of 1 drink/day is allowed during the study.
8. Positive screen for alcohol or drugs of abuse, including phencyclidine, barbiturates, benzodiazepines, opiates, methadone, cocaine, cannabinoids, and amphetamines at screening or Day 1. Subjects who have a positive screen for cannabinoids or other medically prescribed drugs of abuse at screening, must have a negative screen at Day 1 and agree not to use during the study.
9. Any history of schizophrenia or other psychotic disorder, bipolar disorder, psychosis, or other Axis 1 disorder (except for major depressive disorder or anxiety disorders that followed exposure to the trauma or an anxiety disorder that showed a worsening after trauma). Anxiety disorders (such as selective mutism, specific phobia, social anxiety disorder, panic disorder, agoraphobia, and generalized anxiety disorder) are exclusionary only if the diagnosis preceded the primary traumatic event, and, the subject was seeking and received treatment for the symptoms prior to the primary traumatic event. NOTE: A current secondary diagnosis of major depressive disorder without full remission is not exclusionary; if treated, the dose of a permitted antidepressant must be stable for at least 30 days prior to screening and expected to continue during the study.
10. Clozapine use or electroconvulsive therapy within the 12 months prior to screening or during the study.
11. Current use of medications with primarily CNS activity (e.g., antipsychotics, anticonvulsant drugs [including gabapentinoids], psychostimulants, benzodiazepines, methylphenidate, doxazosin, prazosin, clonidine, first-generation sedating H1 antihistamines, quetiapine, eszopiclone, zolpidem extended-release, or any other sedative-hypnotic medications) within 3 days prior to screening or during the study. NOTE: Use of certain non-benzodiazepine sleep

- inducers (e.g., zolpidem immediate-release [up to 10 mg at bedtime], zaleplon [up to 20 mg at bedtime]), melatonin, or ramelteon for sleep are allowed.
12. Use of nefazodone, selective serotonin reuptake inhibitors (SSRIs, such as fluoxetine, sertraline, escitalopram, citalopram, paroxetine), serotonin and norepinephrine reuptake inhibitors (SNRIs, such as desvenlafaxine, duloxetine, venlafaxine), reversible and non-reversible monoamine oxidase inhibitors (such as selegiline, phenelzine, tranylcypromine), tricyclic antidepressants (such as amitriptyline, imipramine, nortriptyline), noradrenergic and specific serotonergic antidepressant (NaSSA) mirtazapine, serotonin modulator and stimulator antidepressants (such as vilazodone or vortioxetine), or the norepinephrine, serotonin and dopamine reuptake inhibitor bupropion within 30 days (90 days for fluoxetine) prior to screening or during the study. **NOTE:** Subjects on stable treatment ( $\geq 30$  days prior to screening) with St. John's Wort may continue this therapy during the study with no expected change in dose.
  13. Treatment with an injectable depot neuroleptic within 90 days prior to screening or during the study.
  14. Subjects who meet the criteria for suicidal intent, plan and/or behavior on the S-STS at screening or Day 1. These criteria are a score of 3 or 4 on questions 2 or 13, or 2 or higher on any of the following questions: 1a (only if 1b is coded YES), 3, 4, 5, 6, 7, 8, 9, 10, 11, 12, or 14.
  15. In the process of litigating for compensation for a psychiatric disorder. Subjects who are in the process of applying for medical or VA benefits and/or those who have settled a disability claim prior to enrollment in the trial are eligible.
  16. History of Huntington's, Parkinson's, and/or Alzheimer's disease, multiple sclerosis, seizures (history of childhood febrile seizures are not exclusionary), epilepsy, or stroke.
  17. History of allergy, sensitivity, or intolerance to N-methyl-D-aspartate receptor (NMDAR) ligands, including ketamine, dextromethorphan, memantine, methadone, dextropropoxyphene, or ketobemidone, as well as current use of such agents.
  18. Received an investigational drug product or device within 30 days (or 5 half-lives, whichever is longer for a drug product) of dosing.
  19. Previously received NYX-783.
  20. Screening QT interval corrected for heart rate (HR) by Fridericia's formula (QTcF)  $>450$  (males) or  $470$  (females) milliseconds (msec) or an ECG that is not suitable for QT measurements (e.g., poorly defined termination of T-wave in the investigator's opinion).
  21. A known familial history or known presence of long QT syndrome, or a known history of past or current clinically significant arrhythmias or ischemic heart disease.
  22. Body mass index  $>35$  kg/m^2 at screening.
  23. HR  $\leq 45$  or  $>95$  beats per minute at screening.
  24. Uncontrolled Type I or Type II diabetes mellitus or uncontrolled hypertension.
  25. Estimated creatinine clearance  $<60$  mL/minute calculated by the Cockcroft-Gault equation at screening or history of renal disease, as assessed by the investigator or the sponsor-designated medical monitor.

26. Known diagnosis of a current infectious disease, including human immunodeficiency virus infection, hepatitis, or other ongoing infectious disease that the investigator considers clinically significant.
27. Current evidence of dysplasia or history of malignancy (including lymphoma and leukemia) in the last 5 years, with the exception of successfully treated non-metastatic basal cell or squamous cell carcinoma of the skin or localized carcinoma in situ of the cervix.
28. History of gastrointestinal disease or surgery (except simple appendectomy or hernia repair), leading to impaired drug absorption.
29. Known abnormal laboratory results, ECG results, medical history or concurrent conditions which, in the opinion of the investigator or sponsor, would preclude safe study participation or interfere with study procedures/assessments.
30. Uncorrected hypothyroidism or hyperthyroidism. NOTE: subjects with compensated hypothyroidism, with normal thyroid-stimulating hormone levels may be enrolled.
31. Impaired hepatic function characterized by a previous known diagnosis of chronic liver disease and/or the presence of direct bilirubin >1.5x, or, alanine transaminase, aspartate transaminase, alkaline phosphatase, or gamma-glutamyl transferase >2x the upper limit of normal at screening.
32. Current borderline personality disorder, antisocial personality disorder, or other personality disorder (e.g. subject showed pervasive pattern of disregard for and violation of the rights of others, or subject has had previous repetitive suicidal behavior [including aborted, interrupted or ineffective suicide attempts, gestures], self-mutilating behavior, or has ever been homicidal) of sufficient severity, in the investigator's opinion, to interfere with study participation.
33. Use of NMDAR-binding drugs (e.g., ketamine, dextromethorphan, memantine, methadone, lamotrigine, esketamine) within 60 days prior to dosing or during the study.
34. 3,4-Methylenemetamphetamine (MDMA)-assisted psychotherapy within 90 days prior to screening or during the study.
35. Expected to initiate any psychotherapy during the study.

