

25. Estimated creatinine clearance <60 mL/minute (calculated by the Cockcroft-Gault equation) at screening or history of renal disease, as assessed by the investigator or the sponsor-designated medical monitor.

26. Known diagnosis of a current infectious disease, including human immunodeficiency virus infection, hepatitis, or other ongoing infectious disease that the investigator considers clinically significant.

27. Current evidence of dysplasia or history of malignancy (including lymphoma and leukemia) in the last 5 years, except for successfully treated non-metastatic basal cell or squamous cell carcinoma of the skin or localized carcinoma in situ of the cervix.

28. History of gastrointestinal disease or surgery (except simple appendectomy or hernia repair), leading to impaired drug absorption.

29. Known abnormal laboratory results, ECG results, medical history or concurrent conditions which, in the opinion of the investigator or sponsor, would preclude safe study participation or interfere with study procedures/assessments.

30. Uncorrected hypothyroidism or hyperthyroidism. NOTE: Subjects with compensated hypothyroidism with normal thyroid-stimulating hormone levels may be enrolled.

31. Impaired hepatic function characterized by a previous known diagnosis of chronic liver disease and/or the presence of direct bilirubin >1.5x, or, alanine transaminase, aspartate transaminase, alkaline phosphatase, or gamma-glutamyl transferase >2x the upper limit of normal at screening.

32. Current borderline personality disorder, antisocial personality disorder, or other personality disorder (e.g. subject showed pervasive pattern of disregard for and violation of the rights of others, or subject has had previous repetitive suicidal behavior [including aborted, interrupted or ineffective suicide attempts, gestures], self-mutilating behavior, or has ever been homicidal) of sufficient severity, in the investigator's opinion, to interfere with study participation.

33. Use of NMDAR-binding drugs (e.g., ketamine, dextromethorphan, memantine, methadone, lamotrigine, esketamine) within 60 days prior to dosing or during the study.

34. 3,4-Methylenedioxymetamphetamine (MDMA)-assisted psychotherapy within 90 days prior to screening or during the study.

35. Expected to initiate any psychotherapy during the study.

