### **9.3. Stage 1: Day 1**

- Medical and psychiatric history updates (if applicable)
- Inclusion/exclusion criteria
- S-STS (since last visit version)
- Vital signs (after at least 5 minutes of rest, sitting or supine)
- Body weight
- ECG (after at least 5 minutes supine rest)
- Concomitant medications
- Laboratory tests
  - Clinical chemistry (fasted)
  - Hematology
  - [REDACTED]
  - [REDACTED]
  - Pregnancy test (urine) for women of childbearing potential
  - Drug (urine) and alcohol screen (breathalyzer)
  - Urinalysis
- Clinical measures (all measures except for CAPS-5 are not required if last measurement is within 14 days prior to Day 1)
  - CAPS-5
  - PCL-5
  - HADS
  - CGI-S
  - PSQI
  - PSQI-A

- [REDACTED]
- DES-II
- BAC-Symbol Coding
- Randomization
- Study drug dispensing, dose administration (in clinic and after completion of above-noted study procedures), and compliance monitoring
  - Medication adherence and reminder system training
- AEs (serious and non-serious)

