#### **12.4.5. Clinical Laboratory Assessments**

The investigator will review clinical laboratory test results as they become available for determination and documentation of clinical significance, if there are any out-of-range values. Abnormal laboratory results at Screening may be repeated for eligibility determination. Possibly drug-related or clinically-relevant abnormal values of uncertain causality must be repeated. Ongoing abnormal laboratory values should be followed at the investigator's discretion.

All women of child-bearing potential will receive serum pregnancy tests ( $\beta$ -HCG) and urine pregnancy tests.

Hepatitis and HIV screen includes: HIV, hepatitis B surface antigen, and hepatitis C antibody.

Hematology includes: White blood cell count with differential (neutrophils, lymphocytes, monocytes, eosinophils, basophils); hemoglobin; hematocrit; mean corpuscular volume (MCV); mean corpuscular hemoglobin (MCH); MCH concentration (MCHC); mean platelet volume (MPV); red blood cell count; red cell distribution width (RDW), and platelet count.

Clinical chemistry includes electrolytes (bicarbonate, calcium, chloride, phosphorus, potassium, sodium, magnesium), enzymes (ALP, AST, ALT, lactate dehydrogenase, gamma-glutamyl transferase), and other tests (albumin, bilirubin [total], direct bilirubin, indirect bilirubin, creatinine, glucose, protein [total], blood urea nitrogen, thyroid stimulating hormone [at screening only], and uric acid).

Qualitative urinalysis includes appearance, color, pH, specific gravity, glucose, ketones, protein, blood, leukocyte esterase, urobilinogen, bilirubin, and nitrites. Microscopy will include red blood cells, white blood cells, epithelial cells, casts, and bacteria.

Standard blood and urine drug panel includes analysis for benzodiazepines, opiates, cocaine, cannabinoids, amphetamines, barbiturates, methadone, and phencyclidine. Serum and alcohol breathalyzer testing will also be performed. The screening period may be extended to ensure washout, if needed, between screening and Day 1.

An estimated creatinine clearance will be calculated.

Refer to the laboratory sample collection, handling, and shipping specifications for additional instruction.

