## **13. STOPPING RULES AND SAFETY MONITORING**

### **13.1. Stopping Rules for Individual Subjects**

Any subject may withdraw consent at any point during the study. The investigator can discontinue a subject at any time if it is deemed medically appropriate, or for subject noncompliance with study requirements. Subjects will be withdrawn from the study if any of the following criteria are met:

- Occurrence of an AE, intercurrent illness, or laboratory abnormality which, in the opinion of the investigator, warrants the subject's permanent withdrawal from the study for subject safety
- Repeated results (i.e., values are confirmed by repeat testing as soon as feasible) showing any of one following laboratory findings:
  - Total bilirubin  $\geq 2.5$  mg/dL
  - ALT or AST  $> 3$  x ULN
  - ALT or AST  $\geq 3$  x ULN and total bilirubin  $\geq 2$  x ULN
  - ALT or AST  $\geq 3$  x ULN, with the appearance of fatigue, nausea, vomiting, right upper quadrant pain, or tenderness, fever, rash, or eosinophilia ( $> 5\%$ )
  - Alkaline phosphatase  $\geq 2$ x ULN
- 2 consecutive ECGs showing a new absolute corrected QT interval (QTc)  $\geq 500$  milliseconds (msec) that was not present on the corresponding baseline ECG, or a QT/QTc interval  $> 60$  msec over the corresponding baseline value. The QT interval should be corrected by Fridericia's (QTcF) formula.

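### Exclusion 31 sets no total bilirubin limit, so unless Exclusion 29 is used a subject can be randomized on a stable value (≥2.5 mg/dL) for which Section 13.1 requires withdrawal

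*Protocol*

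**What the plan says.** **Entry.** Exclusion 31 in Protocol Section 8.2 has two limbs: a previously known diagnosis of chronic liver disease, and a screening result of "direct bilirubin >1.5x, or, alanine transaminase, aspartate transaminase, alkaline phosphatase, or gamma-glutamyl transferase >2x the upper limit of normal at screening". The synopsis carries the same criterion, beginning "Impaired hepatic function characterized by a previous known diagnosis of chronic liver disease and/or the presence of direct bilirubin". Neither place limits total or indirect bilirubin, and no other listed criterion does.

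**Withdrawal.** Section 13.1 makes withdrawal mandatory on "Repeated results (i.e., values are confirmed by repeat testing as soon as feasible) showing any of one following laboratory findings". The list opens with total bilirubin of 2.5 mg/dL or more. It is an absolute value with no reference to baseline. In the same section, the QTc rule at 500 msec applies only to a prolongation "that was not present on the corresponding baseline ECG".

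**Safeguards.** Exclusion 29 covers "Known abnormal laboratory results, ECG results, medical history or concurrent conditions which, in the opinion of the investigator or sponsor", would make participation unsafe or interfere with the study's procedures or assessments. Section 12.4.5 has the investigator review out-of-range results and document their clinical significance. It adds: "Abnormal laboratory results at Screening may be repeated for eligibility determination". Section 9.3 lists "Inclusion/exclusion criteria" again on Day 1.

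**Measurement.** The chemistry panel in Section 12.4.5 includes "other tests (albumin, bilirubin [total], direct bilirubin, indirect bilirubin, creatinine", so total bilirubin is already known at screening.

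**The concern.** An entry criterion should not admit a subject who already meets a mandatory withdrawal rule. Here the two rules use different analytes: entry looks at direct bilirubin, withdrawal at total. A subject whose raised total is almost all indirect, with normal enzymes and no known liver disease, passes Exclusion 31. If the value is stable, the on-study chemistry and its repeat will confirm it, and Section 13.1 then leaves no discretion.

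Such a subject is exposed to study drug or placebo and then withdrawn for a result that was available before randomization. Section 8.4 says withdrawn subjects are not replaced. If the subject is on an active dose, the case also enters the count of five that Section 13.2 uses for a dosing stop on that regimen.

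**Working it through.** The plan gives no figure to reproduce. The check sets the two sets of limits side by side, asks whether the gap can occur, and bounds its size.

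**1. Entry and withdrawal limits (Protocol 8.2 and 13.1)**

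| Measure | Excluded at screening | Withdrawn on study | Can a subject enter on a withdrawal value? |
|---|---|---|---|
| ALT, AST | >2x ULN | >3x ULN | No |
| ALP | >2x ULN | ≥2x ULN | Only at exactly 2x |
| QTcF | >450 (men) or >470 (women) msec | new value ≥500 msec, or >60 msec over baseline | No |
| Direct bilirubin | >1.5x ULN | no rule | Not applicable |
| Total bilirubin | no limit | ≥2.5 mg/dL | Yes |

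Total bilirubin is the only one of these measures with a withdrawal limit and neither an entry limit nor a baseline condition.

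**2. Can it occur?** Indirect = total − direct. The documents give no ULN for direct bilirubin, so assume 0.2 to 0.5 mg/dL.
- Highest direct value that Exclusion 31 allows: 1.5 × 0.2 = 0.30, up to 1.5 × 0.5 = 0.75 mg/dL.
- Indirect bilirubin needed for a total of 2.5: 2.5 − 0.30 = 2.20, down to 2.5 − 0.75 = 1.75 mg/dL.

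No criterion limits indirect bilirubin, so the combination passes Exclusion 31.

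**3. How many?** Let p be the proportion of otherwise eligible subjects with total ≥2.5 mg/dL and direct ≤1.5x ULN. The documents do not give p; the range below is an assumption. The planned sample is N = 156. Randomization at 4:1:1 puts 156 × 1/6 = 26 on each active dose in Stage 1. The 15% Stage 1 dropout assumption allows for 0.15 × 156 = 23.4 subjects.

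| p | 0.1% | 0.5% | 1% | 2% |
|---|---|---|---|---|
| Upper bound, 156p (Exclusion 29 never used, every value confirmed) | 0.16 | 0.78 | 1.56 | 3.12 |
| Exclusion 29 catches half, 78p | 0.08 | 0.39 | 0.78 | 1.56 |
| Chance that none is enrolled, (1 − p)^156 | 85.5% | 45.8% | 20.8% | 4.3% |
| Upper bound as share of 23.4 | 0.7% | 3.3% | 6.7% | 13.3% |
| Chance of ≥5 among 26, binomial | 0.000000006% | 0.00002% | 0.0006% | 0.015% |
| Extra screen failures under a cap, 156p/(1 − p) | 0.16 | 0.78 | 1.58 | 3.18 |

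The row for five or more uses Stage 1 only, because a stable case should be found and withdrawn before re-randomization.

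**The case against.** **Exclusion 29 is broader than a safety clause.** It also reaches results that would interfere with study procedures or assessments, and either the investigator or the sponsor can invoke it. A value that already requires withdrawal fits that description. With the documented review of out-of-range results in Section 12.4.5, enrolment would mean that someone saw the value and passed over it. This stands, and it makes the gap smaller. It does not close it: the criterion rests on opinion, no safeguard names a total bilirubin limit, and a clinician could reasonably judge a stable indirect elevation harmless.

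**The choice may be deliberate.** All the hepatic rules in Section 13.1 are absolute, so the contrast with QTc is weak evidence of an oversight. Limiting direct bilirubin while measuring all three fractions is consistent with wanting to admit isolated indirect elevation. That is possible. But Section 13.1 would then withdraw those of the admitted subjects who are at or above 2.5 mg/dL, so the two rules conflict under either intention.

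**The consequences are limited.** The Early Termination visit (Section 9.8) collects CAPS-5 and the other clinical measures. Section 13.2 makes a dosing stop depend on unblinded DSMB review, which could recognise an unchanged pre-existing value. Section 14.2 lets the sample size be adjusted for excess dropout. All of this stands.

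**Stronger readings to avoid.** A reader might infer that nothing in the protocol would keep such a subject out; Exclusion 29 can. A reader might also infer that these withdrawals bias the primary comparison or threaten a study stop. The documents do not support that: a withdrawal on an unchanged value does not depend on CAPS-5 response, and the binomial figures put five cases on one dose below 0.02%.

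**A cap at 2.5 mg/dL leaves no margin.** ALT and AST have one (2x at entry, 3x at withdrawal). Also, Table 4, note q, exempts screening chemistry from fasting, so screening and on-study values are not taken under the same conditions. Both points stand and shape the fix.

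**Conclusion.** The rules conflict, and the conflict is minor. Applied as written, Exclusion 31 and Section 13.1 together can enrol, dose and then withdraw a subject on an unchanged screening value, unless Exclusion 29 is used. The text alone establishes this.

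The size is uncertain because it depends on an assumed prevalence. Over 0.1% to 2% it is at most 0.16 to 3.1 of 156 subjects, and about half that if Exclusion 29 catches half of the cases. At the low end, most likely no such subject is enrolled. No power figure, error rate or conclusion of the trial changes. The reason to act is to avoid a foreseeable and pointless exposure and withdrawal. This is a point to consider; confidence is medium.

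**What to change.** Add total bilirubin ≥2.5 mg/dL at screening to the laboratory values listed in Exclusion 31, in Section 8.2 and in the synopsis. Leave Sections 13.1 and 13.2 unchanged. Ask sites to repeat a raised screening total bilirubin fasted, so that it is comparable with on-study values; Section 12.4.5 already permits the repeat.

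This stops enrolment on a value that already requires withdrawal. It does not prevent later withdrawal of a subject who enters just below 2.5 mg/dL and drifts over it.

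If the sponsor meant to admit isolated indirect elevation, the alternative is to require in Section 13.1 that the value was not present at baseline. That loosens hepatic monitoring for a drug whose liver findings in dogs at 20 mg/kg were adverse and did not recover (Section 5), so the entry cap is preferable.

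**Cost.** No new test is needed, apart from the occasional fasted repeat. Expect 0.2 to 3.2 extra screen failures per 156 enrolled under the assumed range, and fewer where Exclusion 29 would have applied anyway. If their values persist, those subjects would have to be withdrawn under the current Section 13.1. Under Section 15.4 each site submits an amendment to its IRB, with up to about 30 sites planned, so the wording should go into the next amendment and does not justify one of its own.
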